9.8. Quality Control

Upon initiation of analyses, edit, range, and logic checks will be performed on each data field by the project programmer to ensure the quality and completeness of the study database and all of the variables therein. Only observed data will be used in measuring study variables. It is anticipated that demographic information will be available for nearly all individuals in the study population. All other variables will be defined based on the presence of specific data (e.g., diagnosis, procedure, and drug codes) in the analytic file; the absence of such data will be assumed to indicate the absence of the characteristic/event captured by the variable.

9.9. Limitations of the Research Methods

There are several limitations in this study. Given that this is an observational study using health care administrative claims data, residual confounding due to missing or unmeasured information is possible. To examine this, we will assess the effect of PCV13 on a negative control outcome and the effect of a negative control exposure on our outcomes of interest. If the HRs in any of these models are less than 1.0, it would indicate that residual confounding exists and may result in adjustment of our VE estimates.

Second, health care administrative claims data will be available from January 1, 2014 through September 30, 2022. The recommendation to vaccinate all PLWH was published in June 2012, and some PLWH may have received PCV13 prior to January 1, 2014 and be misclassified as unvaccinated. In addition, PLWH eligible for the study may have received PCV13 vaccination during a time period in which we do not have their claims data. Misclassification of PCV13 vaccine status may lead to lower estimates of vaccine effectiveness than in truth, because our unvaccinated cohort will incorrectly include vaccinated PLWH.

In addition, we are using ICD-9-CM and ICD-10-CM codes to define HIV infection. Our definition of HIV infection requires at least one HIV-related diagnosis code in the inpatient setting or at least two HIV-related diagnosis codes in the outpatient setting. While this definition of HIV has been used in previous administrative claims database studies, it is possible that these codes may be used by health care providers to order laboratory tests to rule out HIV infection and thus, some individuals without HIV will be included in our study population.

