Several stratified analyses will be conducted. PPSV23 is recommended for PLWH and feasibility data provided by Komodo suggest that one in four PWLH who received PCV13 during 2014-2015 also received PPSV23 within two years. Rather than censor or exclude

individuals who receive PPSV23, we will calculate PCV13 VE among PWLH who have/have not received PPSV23 before and during the study period.

Feasibility assessments from Komodo indicate that approximately 25% of PWLH have at least one CD4 cell count or percentage laboratory result available. Therefore, we will calculate PCV13 VE among the subset of PWLH who have a CD4 cell count during the baseline period or follow-up, and potentially stratify by CD4 category using each patient's lowest value during the study.

Additional VE stratifications by ART adherence during follow-up, year of HIV diagnosis, and age will be assessed for feasibility as well, as these affect patients' immune status and immune reconstitution. Due to possible waning of the VE and different lengths of follow-up by index year, VE stratification by year of HIV diagnosis will be restricted to the first 3 years of follow-up.

A sensitivity analysis will also be conducted. In this analysis, causes of pneumonia that are characteristic of HIV, for example pneumonia due to cytomegalovirus, mycobacteria, and fungi, will be excluded from our definition of all-cause pneumonia.

Residual confounding of our VE estimates due to inadequate control for health care seeking behavior and immune status in our analyses will be explored. To do so, we will employ a negative control exposure and a negative control outcome. Potential negative control exposures include vaccinations that are recommended for PLWH but would not be expected to have any protective effect against the pneumonia outcomes of interest. If residual confounding does not exist, the negative control vaccine would not have an effect on the pneumonia outcomes. However, if the analysis demonstrates that the negative control vaccine protects against these outcomes, this suggests the presence of residual confounding.

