### 5.3.3. Negative Controls

**Table 5.4 List of Negative Control Variables**

Variable	Operational Definition	Role	Time of Use
Recombinant zoster vaccine (RZV; Shingrix, GlaxoSmithKline)	NDC and CPT codes listed in Appendix Table 7.10	Negative control exposure	Follow-up
May include, but not limited to, candidiasis infection, all-cause diarrhea and accidental injury	ICD-9-CM and ICD-10-CM codes listed in Protocol Annex Table 4.1  Candidiasis infection: evidence of an antifungal treatment within 7 days of outpatient candidiasis ICD-9-CM or ICD-10-CM codes will be explored. NDC and CPT codes listed in Appendix Table 7.13	Negative control outcomes	Follow-up

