#### **5.8.8. Assessment of Residual Confounding**

*Residual confounding of our VE estimates due to inadequate control for health care seeking behavior and immune status in our analyses will be explored. To do so, we will employ a negative control exposure and a negative control outcome. Potential negative control exposures include vaccinations that are recommended for PLWH but would not be expected to have any protective effect against the pneumonia outcomes of interest. We plan to use recombinant zoster vaccine (RZV) as the negative control exposure. Current US clinical guidelines recommend that PLWH be offered RZV vaccination. Therefore, we will develop a*

*model for our study population in which the exposure is at least one dose of RZV and the outcomes are our primary outcomes of interest. If residual confounding does not exist, RZV would not have an effect on the pneumonia outcomes. However, if the analysis demonstrates that RZV protects against these outcomes, this suggests the presence of residual confounding. Patients who have evidence of RZV during the six-month baseline period will be excluded from the negative control exposure analysis.*

*Similarly, potential negative control outcomes are outcomes that share the same sources of biases as the primary outcomes in our study population but are not causally-related to PCV13 vaccination. For example, immune status is an important predictor of pneumonia outcomes among PLWH, but we will be missing CD4 laboratory values for most of our study population. In order to detect potential residual confounding by lack of control for immune status, a potential negative control outcome could include a more common AIDS defining illness such as candidiasis. Again, if no residual confounding exists, PCV13 vaccination would have no effect on the occurrence of the negative control outcomes. However, if the results suggest that PCV13 vaccination prevents the negative control outcomes, residual confounding may exist.*

If the negative control outcome analysis indicates residual confounding, the results of the main outcomes may be additionally reported after correcting for the bias [12].

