#### 5.8.12. Analysis of Negative Control Outcomes and Exposure

The number of patients with the negative control outcome(s) will be presented by PCV13 vaccination status at the time of occurrence. Crude incidence rates and 95% CIs will be presented by PCV13 status for first and recurrent (separated by at least 90 days) episodes. Unadjusted and Cox-MSM will be used to obtain crude and weighted VE estimates and 95% CIs of PCV13 on candidiasis.

The number of patients who receive at least one dose of RZV by the end of the overall follow-up will be reported. Patients will be considered vaccinated with RZV 14 days after their vaccination date. Unadjusted and Cox-MSM will be used to obtain crude and weighted VE estimates and 95% CIs of RZV on each of the study outcomes of interest. Cox-MSM will additionally adjust for the main exposure of PCV13 as a time-varying covariate. Patients who have evidence of RZV before the six-month baseline period will be excluded from the negative control exposure analysis.

Weighted 95% CIs for the VEs that exclude 0% would suggest the presence of residual confounding in the weighted models between PCV13 and the study outcomes. If so, the results for the main outcomes may be corrected for bias identified from the negative control outcome.

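### Protocol 9.9 reads any negative-control hazard ratio below 1.0 as residual confounding, SAP 5.8.12 goes by the 95% CI, and the SAP gives two different RZV exclusions

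*Protocol*

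**What the plan says.** **Trigger.** Protocol 9.9 (Limitations) covers two kinds of model: PCV13 on a negative control outcome, and a negative control exposure on the study outcomes. Its rule is: "If the HRs in any of these models are less than 1.0, it would indicate that residual confounding exists". It adds that this "may result in adjustment of our VE estimates". No precision condition is attached, and hazard ratios above 1.0 are not mentioned.

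Protocol 9.7 gives no numerical cut-off; it says "if the analysis demonstrates that the negative control vaccine protects against these outcomes, this suggests the presence of residual confounding".

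SAP 5.8.12 sets an interval rule: "Weighted 95% CIs for the VEs that exclude 0% would suggest the presence of residual confounding in the weighted models". Since VE is 1 minus the HR, a VE of 0% is an HR of 1.0, and the interval can exclude it on either side. On consequences, SAP 5.8.8 says: "If the negative control outcome analysis indicates residual confounding, the results of the main outcomes may be additionally reported after correcting for the bias". SAP 5.8.12 likewise takes any correction from the negative control outcome.

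**RZV exclusion.** SAP 5.8.8: "Patients who have evidence of RZV during the six-month baseline period will be excluded from the negative control exposure analysis". SAP 5.8.12: "Patients who have evidence of RZV before the six-month baseline period will be excluded from the negative control exposure analysis". The current protocol has no RZV exclusion.

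**The concern.** The protocol and SAP say that CD4 values will be missing for most of the population, so the negative controls carry much of the weight in judging whether a VE estimate can be believed. Two things go wrong.

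First, the same negative-control result can be called confounding under one document and not under the other. The Protocol 9.9 rule also ignores sampling error, so it will often report confounding where there is none. If the rule is not settled in advance, it can be chosen after the results are known.

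Second, the two RZV sentences name different groups. Under 5.8.8 alone, people given RZV only before the baseline period stay in. Under 5.8.12 alone, people given it during the baseline period stay in. SAP Table 5.4 lists RZV for use in follow-up only, so earlier recipients could be counted as unexposed. That would dilute the RZV contrast and could hide the bias it is meant to reveal.

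**Working it through.** Neither document gives an error rate or precision figure for the negative-control analyses, so there is no stated figure to reproduce. The check compares how the two rules behave.

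**1. False flags with no confounding (true HR = 1, log HR estimate symmetric about 0)**

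- Per model: P(HR < 1.0) = 0.50; P(95% CI excludes VE 0%) = 0.05.
- Number of models: SAP 5.8.8 applies RZV to the primary outcomes (three), and I add one negative control outcome, giving four.
- Dependence is unknown. The limits are all four independent, or the three RZV models fully dependent (acting as one) and independent of the outcome model.

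| Rule | Per model | RZV models fully dependent | All four independent |
|---|---|---|---|
| Protocol 9.9 | 50% | 1 − 0.5² = 75% | 1 − 0.5⁴ = 93.8% |
| SAP 5.8.12 | 5% | 1 − 0.95² = 9.8% | 1 − 0.95⁴ = 18.5% |

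For the single negative control outcome model, the only one from which the SAP would take a correction, the SAP rate is 5%.

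**2. Can the rules disagree in both directions?**

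Protocol Table 2 (IPD, 97 months, 4% censoring, VE 7.5%) gives a VE interval of −5 to 19. The implied standard error is (ln 1.05 − ln 0.81)/3.92 = 0.066. Two illustrative results with that SE:

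- HR 0.97, CI 0.97·exp(∓1.96 × 0.066) = 0.85 to 1.10: confounding under Protocol 9.9, not under the SAP.
- HR 1.15, CI 1.01 to 1.31: confounding under the SAP, not under Protocol 9.9.

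**3. How much bias would the interval rule detect?**

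The smallest spurious VE whose interval excludes 0 is 1 − exp(−1.96 × SE).

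- PCV13 on a negative control outcome as rare as IPD: SE 0.066, threshold about 12%.
- The same model with an outcome as common as all-cause pneumonia (Table 3, same follow-up and censoring, VE 5%, interval 2 to 7): SE = (ln 0.98 − ln 0.93)/3.92 = 0.0134, threshold 2.6%, about 3%.
- RZV models: the documents give no uptake, so I assume 2%, 5% or 10% of events fall in exposed time. SE = √(1/d₁ + 1/d₀), where d₁ and d₀ are events in exposed and unexposed time.

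| Outcome (total events) | 2% | 5% | 10% |
|---|---|---|---|
| IPD (1,492): d₁ | 30 | 75 | 149 |
| Threshold | 30% | 21% | 16% |
| All-cause pneumonia (38,848): d₁ | 777 | 1,942 | 3,885 |
| Threshold | 6.9% | 4.5% | 3.3% |

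The interval rule is therefore insensitive for rare outcomes such as IPD, but not for all-cause pneumonia.

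**4. RZV exclusion**

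This is a comparison of text. The two windows do not overlap. Together they cover all time before the index date; separately, each leaves a gap. The size of either group is not given, so the effect cannot be quantified.

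**The case against.** The strongest reply is that the hierarchy is already clear. Protocol 9.7 leaves detailed methodology to the SAP and lets it modify the protocol, so an analyst following the SAP has one interval rule, and the 9.9 sentence is only a remark under limitations. That is a fair reading. But the SAP nowhere says that it replaces the 9.9 rule. The two documents are dated one day apart (6 and 7 December 2023), and 9.9 is current text that names a consequence for VE.

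The consequences are also soft. The SAP says its criterion would suggest confounding, and correction is optional in both documents. This stands, and it limits the severity.

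The model count of four is a choice. SAP 5.8.12 refers to the study outcomes of interest, of which Table 5.2 lists five as primary or secondary, and Table 5.4 leaves the negative control outcomes open ("May include, but not limited to, candidiasis infection, all-cause diarrhea and accidental injury"). Four is at the low end: with six independent models the rates are 98.4% and 26.5%. If all models moved together they would be 50% and 5%. The contrast between the rules survives any count.

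The detection thresholds are approximate. They ignore weighting and robust variances, the RZV shares are assumed, and the outcomes named in Table 5.4 may well be more common than IPD. It also stands that a wide interval including 0% does not show that confounding is absent.

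Finally, the two RZV sentences can be applied together, since neither claims to be the only exclusion. That is probably the intent, but it should be written down.

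**Conclusion.** The point holds on both parts. The rules differ in threshold (point estimate against interval), in direction (below 1.0 only against either side) and in which model can lead to a correction (any negative-control model against the negative control outcome). With no confounding, the Protocol 9.9 rule gives a false flag half the time per model and 75% to 94% of the time over four models; the SAP rule gives 5% and 10% to 19%. These figures assume a symmetric log HR estimate and the stated dependence limits.

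The RZV sentences name different groups, and the effect of following only one cannot be sized from the documents.

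The primary VE models are not touched, and the SAP would show a corrected VE in addition to the uncorrected one. What is at stake is how the VE is interpreted and whether a corrected figure is reported. It should be fixed before results are interpreted.

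**What to change.** - **Protocol 9.9:** delete the below-1.0 trigger and refer to SAP 5.8.12. State that negative-control HRs are reported with 95% CIs, that they are judged on the interval in either direction, and that any correction comes from the negative control outcome, with corrected VE shown beside uncorrected VE. Protocol 9.7 and SAP 5.8.8 describe only a spurious protective effect, so the new sentence should make clear that this wording does not limit the rule.
- **SAP 5.8.8 and 5.8.12:** use the same sentence in both, excluding anyone with evidence of RZV at any time before the index date.
- **Optional:** because Table 5.4 allows several negative control outcomes, name in advance the one that supplies the correction.

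The cost is one sentence in the protocol and one in each SAP section, with no new data or models. Protocol 9.6 requires the sponsor's approval and all collaborators' agreement for amendments. The RZV cohort becomes slightly smaller.

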9.10. Other Aspects

Not applicable

10. PROTECTION OF HUMAN PARTICIPANTS

10.1. Patient Information

This study involves data that exist in deidentified/anonymized structured format and contain no patient personal information.

10.2. Patient Consent

As this study involves deidentified/anonymized structured data, which according to applicable legal requirements do not contain data subject to privacy laws, obtaining informed consent from patients by Pfizer is not required.

10.3. Institutional Review Board (IRB)/Ethics Committee (EC)

The study databases will be de-identified prior to their release to study investigators, as set forth in the corresponding Data Use Agreement. The study databases have been evaluated and certified by an independent third party to be compliant with the Health Insurance Portability and Accountability Act (HIPAA) of 1996 statistical de-identification standards and to satisfy the conditions set forth in Sections 164.514 (a)-(b)1ii of the HIPAA Privacy Rule regarding the determination and documentation of statistically de-identified data. Use of the study databases for health services research is therefore fully compliant with the HIPAA Privacy Rule and federal guidance on Public Welfare and the Protection of Human Subjects (45 Code of Federal Regulations [CFR] 46 §46.101) and IRB approval is not required.

10.4. Ethical Conduct of the Study

The study will be conducted in accordance with legal and regulatory requirements, as well as with scientific purpose, value and rigor and follow generally accepted research practices described in *Good Pharmacoepidemiology Practices* (GPP) issued by the International Society for Pharmacoepidemiology (ISPE), Good Epidemiological Practice (GEP) guidelines issued by the International Epidemiological Association (IEA), Good Outcomes Research Practices issued by the International Society for Pharmacoeconomics and Outcomes Research (ISPOR), International Ethical Guidelines for Epidemiological Research issued by the Council for International Organizations of Medical Sciences (CIOMS), European Medicines Agency (EMA) European Network of Centres for Pharmacoepidemiology and Pharmacovigilance (ENCEPP) Guide on Methodological Standards in Pharmacoepidemiology, and Food and Drug Administration (FDA) Guidance for Industry: Good Pharmacovigilance and Pharmacoepidemiologic Assessment, and FDA Draft Guidance for Industry and FDA Staff: Best Practices for Conducting and Reporting of Pharmacoepidemiologic Safety Studies Using Electronic Healthcare Data Sets and/or equivalent.

11. MANAGEMENT AND REPORTING OF ADVERSE EVENTS/ADVERSE REACTIONS

This study involves data that exist as structured data by the time of study start. In these data sources, individual patient data are not retrieved or validated, and it is not possible to link (i.e., identify a potential association between) a particular product and medical event for any individual. Thus, the minimum criteria for reporting an adverse event (AE) (i.e., identifiable patient, identifiable reporter, a suspect product, and event) cannot be met.

12. PLANS FOR DISSEMINATING AND COMMUNICATING STUDY RESULTS

Formal communication of the results of this research will be done by study investigators through peer-reviewed publications. For all publications relating to the Study, Pfizer will comply with recognized ethical standards concerning publications and authorship, including

PFIZER CONFIDENTIAL

CT24-WI-GL02-RF02 5.0 Non-Interventional Study Protocol Template For Secondary Data Collection Study

01-Aug-2023

Page 26 of 46

Section II - "Ethical Considerations in the Conduct and Reporting of Research" of the Uniform Requirements for Manuscripts Submitted to Biomedical Journals, <http://www.icmje.org/index.html#authorship>, established by the International Committee of Medical Journal Editors.

In the event of any prohibition or restriction imposed (e.g., clinical hold) by an applicable competent authority in any area of the world, or if the investigator is aware of any new information which might influence the evaluation of the benefits and risks of a Pfizer product, Pfizer should be informed immediately.

16. APPENDIX

Table 1. Diagnosis Codes for Identifying HIV infection

Code	Type	Description
042	ICD-9-CM	HIV-1 infection
V08	ICD-9-CM	Asymptomatic HIV disease
B20	ICD-10-CM	HIV-1 infection
Z21	ICD-10-CM	Asymptomatic HIV disease

Table 2. National Drug Codes for Identifying HIV Antiretrovirals (see excel)

Table 3. National Drug Codes and CPT® Codes for Identifying PCV13 Vaccination

Code	Type	Description
50090194409	NDC	13-valent pneumococcal conjugate vaccine
54569661300	NDC	13-valent pneumococcal conjugate vaccine

PFIZER CONFIDENTIAL

CT24-WI-GL02-RF02 5.0 Non-Interventional Study Protocol Template For Secondary Data Collection Study

01-Aug-2023

Page 29 of 46

50090194400	NDC	13-valent pneumococcal conjugate vaccine
00005197105	NDC	13-valent pneumococcal conjugate vaccine
00005197104	NDC	13-valent pneumococcal conjugate vaccine
00005197102	NDC	13-valent pneumococcal conjugate vaccine
00005197101	NDC	13-valent pneumococcal conjugate vaccine
90670	CPT	13-valent pneumococcal conjugate vaccine

Table 5. Diagnosis Codes for Identifying Pneumococcal Pneumonia and Pneumonia with Unspecified Causes

Condition	ICD-9-CM		ICD-10-CM	
	Codes	Description	Codes	Description
Pneumococcal pneumonia	481	Pneumococcal pneumonia	J13	Pneumonia due to Streptococcus pneumoniae
	482.9 + 041.2	Bacterial pneumonia, unspecified + pneumococcus	J15.9 + B95.3	Unspecified bacterial pneumonia + Streptococcus pneumoniae
	485 + 041.2	Bronchopneumonia, organism unspecified + pneumococcus	J18.0 + B95.3	Bronchopneumonia, unspecified organism + Streptococcus pneumoniae
	486 + 041.2	Pneumonia, organism unspecified + pneumococcus	J18.8 + B95.3 J18.9 + B95.3	Other pneumonia, unspecified organism + Streptococcus pneumoniae Pneumonia, unspecified organism + Streptococcus pneumoniae
	510.x + 041.2			Empyema + pneumococcus
	510 + 041.2	Empyema with fistula + pneumococcus	J86.0 + B95.3	Pyothorax with fistula + Streptococcus pneumoniae
	510.9 + 041.2	Empyema without mention of fistula + pneumococcus	J86.9 + B95.3	Pyothorax without fistula + Streptococcus pneumoniae
Pneumonia with unspecified causes	480-486 487.0			Viral, bacterial, unspecified pneumonia
	480.9	Viral pneumonia, unspecified	J12.9	Viral pneumonia, unspecified
	482.9	Bacterial pneumonia, unspecified	J15.9	Unspecified bacterial pneumonia
	485	Bronchopneumonia, organism unspecified	J18.0	Bronchopneumonia, unspecified organism
	486	Pneumonia, organism unspecified	J18.8 J18.9	Other pneumonia, unspecified organism Pneumonia, unspecified organism

PFIZER CONFIDENTIAL

CT24-WI-GL02-RF02 5.0 Non-Interventional Study Protocol Template For Secondary Data Collection Study 01-Aug-2023

Page 31 of 46

Table 4. Diagnosis Codes for Identifying Invasive Pneumococcal Disease, All-Cause Pneumonia, and Pneumococcal Pneumonia

Condition	ICD-9-CM		ICD-10-CM	
	Codes	Description	Codes	Description
IPD				
Bacteremia	790.7 + 041.2 771.83 + 041.2	Bacteremia + pneumococcus	R78.81 + B95.3	Bacteremia + Streptococcus pneumoniae as the cause of diseases classified elsewhere (Streptococcus pneumoniae)
	038.2	Pneumococcal septicemia	A40.3	Sepsis due to Streptococcus pneumoniae
	038.9 + 041.2	Unspecified septicemia + pneumococcus	A41.9 + B95.3	Sepsis, unspecified organism + Streptococcus pneumoniae
Meningitis	320.1	Pneumococcal meningitis	G00.1	Pneumococcal meningitis
	320.9 + 041.2	Meningitis due to unspecified bacterium + pneumococcus	G00.9 + B95.3 G04.2 + B95.3	Bacterial meningitis, unspecified + Streptococcus pneumoniae Bacterial meningoencephalitis and meningomyelitis, not elsewhere classified + Streptococcus pneumoniae
	322.9 + 041.2	Meningitis, unspecified + pneumococcus	G03.9 + B95.3	Meningitis, unspecified + Streptococcus pneumoniae
Other	421.x + 041.2	Endocarditis + pneumococcus		
	421 + 041.2	Acute and subacute bacterial endocarditis + pneumococcus	I33.0 + B95.3	Acute and subacute infective endocarditis + Streptococcus pneumoniae
	421.1 + 041.2	Acute and subacute infective endocarditis in diseases classified elsewhere + pneumococcus	I39 + B95.3	Endocarditis and heart valve disorders in diseases classified elsewhere + Streptococcus pneumoniae
	421.9 + 041.2	Acute endocarditis, unspecified + pneumococcus	I33.9 + B95.3	Acute and subacute endocarditis, unspecified + Streptococcus pneumoniae
	711.0 + 041.2	Septic arthritis + pneumococcus	M00.00 + B95.3 M00.20 + B95.3 M00.80 + B95.3 M00.9 + B95.3 M00.10 + B95.3	Staphylococcal arthritis, unspecified joint + Streptococcus pneumoniae Other streptococcal arthritis, unspecified joint + Streptococcus pneumoniae Arthritis due to other bacteria, unspecified joint + Streptococcus pneumoniae Pyogenic arthritis, unspecified + Streptococcus pneumoniae Pneumococcal arthritis, unspecified joint + Streptococcus pneumoniae

PFIZER CONFIDENTIAL

CT24-WI-GL02-RF02 5.0 Non-Interventional Study Protocol Template For Secondary Data Collection Study 01-Aug-2023

Page 32 of 46

	711.01 + 041.2	Pyogenic arthritis, shoulder region + pneumococcus	M00.011 + B95.3 M00.012 + B95.3 M00.019 + B95.3 M00.211 + B95.3 M00.212 + B95.3 M00.219 + B95.3 M00.811 + B95.3 M00.812 + B95.3 M00.819 + B95.3 M00.119 + B95.3 M00.111 + B95.3 M00.112 + B95.3	Staphylococcal arthritis, right shoulder + Streptococcus pneumoniae Staphylococcal arthritis, left shoulder + Streptococcus pneumoniae Staphylococcal arthritis, unspecified shoulder + Streptococcus pneumoniae Other streptococcal arthritis, right shoulder + Streptococcus pneumoniae Other streptococcal arthritis, left shoulder + Streptococcus pneumoniae Other streptococcal arthritis, unspecified shoulder + Streptococcus pneumoniae Arthritis due to other bacteria, right shoulder + Streptococcus pneumoniae Arthritis due to other bacteria, left shoulder + Streptococcus pneumoniae Arthritis due to other bacteria, unspecified shoulder + Streptococcus pneumoniae Pneumococcal arthritis, unspecified shoulder + Streptococcus pneumoniae Pneumococcal arthritis, right shoulder + Streptococcus pneumoniae Pneumococcal arthritis, left shoulder + Streptococcus pneumoniae
	711.02 + 041.2	Pyogenic arthritis, upper arm + pneumococcus	M00.021 + B95.3 M00.022 + B95.3 M00.029 + B95.3 M00.221 + B95.3 M00.222 + B95.3 M00.229 + B95.3 M00.821 + B95.3 M00.822 + B95.3 M00.829 + B95.3 M00.129 + B95.3 M00.121 + B95.3 M00.122 + B95.3	Staphylococcal arthritis, right elbow + Streptococcus pneumoniae Staphylococcal arthritis, left elbow + Streptococcus pneumoniae Staphylococcal arthritis, unspecified elbow + Streptococcus pneumoniae Other streptococcal arthritis, right elbow + Streptococcus pneumoniae Other streptococcal arthritis, left elbow + Streptococcus pneumoniae Other streptococcal arthritis, unspecified elbow + Streptococcus pneumoniae Arthritis due to other bacteria, right elbow + Streptococcus pneumoniae Arthritis due to other bacteria, left elbow + Streptococcus pneumoniae Arthritis due to other bacteria, unspecified elbow + Streptococcus pneumoniae Pneumococcal arthritis, unspecified elbow + Streptococcus pneumoniae Pneumococcal arthritis, right elbow + Streptococcus pneumoniae Pneumococcal arthritis, left elbow + Streptococcus pneumoniae
	711.03 + 041.2	Pyogenic arthritis, forearm + pneumococcus	M00.031 + B95.3 M00.032 + B95.3 M00.039 + B95.3 M00.231 + B95.3 M00.232 + B95.3 M00.239 + B95.3 M00.831 + B95.3 M00.832 + B95.3 M00.839 + B95.3 M00.139 + B95.3 M00.131 + B95.3 M00.132 + B95.3	Staphylococcal arthritis, right wrist + Streptococcus pneumoniae Staphylococcal arthritis, left wrist + Streptococcus pneumoniae Staphylococcal arthritis, unspecified wrist + Streptococcus pneumoniae Other streptococcal arthritis, right wrist + Streptococcus pneumoniae Other streptococcal arthritis, left wrist + Streptococcus pneumoniae Other streptococcal arthritis, unspecified wrist + Streptococcus pneumoniae Arthritis due to other bacteria, right wrist + Streptococcus pneumoniae Arthritis due to other bacteria, left wrist + Streptococcus pneumoniae Arthritis due to other bacteria, unspecified wrist + Streptococcus pneumoniae Pneumococcal arthritis, unspecified wrist + Streptococcus pneumoniae Pneumococcal arthritis, right wrist + Streptococcus pneumoniae Pneumococcal arthritis, left wrist + Streptococcus pneumoniae
	711.04 + 041.2	Pyogenic arthritis, hand + pneumococcus	M00.041 + B95.3 M00.042 + B95.3 M00.049 + B95.3 M00.241 + B95.3 M00.242 + B95.3 M00.249 + B95.3 M00.841 + B95.3	Staphylococcal arthritis, right hand + Streptococcus pneumoniae Staphylococcal arthritis, left hand + Streptococcus pneumoniae Staphylococcal arthritis, unspecified hand + Streptococcus pneumoniae Other streptococcal arthritis, right hand + Streptococcus pneumoniae Other streptococcal arthritis, left hand + Streptococcus pneumoniae Other streptococcal arthritis, unspecified hand + Streptococcus pneumoniae Arthritis due to other bacteria, right hand + Streptococcus pneumoniae

PFIZER CONFIDENTIAL

CT24-WI-GL02-RF02 5.0 Non-Interventional Study Protocol Template For Secondary Data Collection Study 01-Aug-2023

Page 33 of 46

			M00.842 + B95.3 M00.849 + B95.3 M00.149 + B95.3 M00.141 + B95.3 M00.142 + B95.3	Arthritis due to other bacteria, left hand + Streptococcus pneumoniae Arthritis due to other bacteria, unspecified hand + Streptococcus pneumoniae Pneumococcal arthritis, unspecified hand + Streptococcus pneumoniae Pneumococcal arthritis, right hand + Streptococcus pneumoniae Pneumococcal arthritis, left hand + Streptococcus pneumoniae
711.05 + 041.2	Pyogenic arthritis, pelvic region and thigh + pneumococcus		M00.051 + B95.3 M00.052 + B95.3 M00.059 + B95.3 M00.251 + B95.3 M00.252 + B95.3 M00.259 + B95.3 M00.851 + B95.3 M00.852 + B95.3 M00.859 + B95.3 M00.159 + B95.3 M00.151 + B95.3 M00.152 + B95.3	Staphylococcal arthritis, right hip + Streptococcus pneumoniae Staphylococcal arthritis, left hip + Streptococcus pneumoniae Staphylococcal arthritis, unspecified hip + Streptococcus pneumoniae Other streptococcal arthritis, right hip + Streptococcus pneumoniae Other streptococcal arthritis, left hip + Streptococcus pneumoniae Other streptococcal arthritis, unspecified hip + Streptococcus pneumoniae Arthritis due to other bacteria, right hip + Streptococcus pneumoniae Arthritis due to other bacteria, left hip + Streptococcus pneumoniae Arthritis due to other bacteria, unspecified hip + Streptococcus pneumoniae Pneumococcal arthritis, unspecified hip + Streptococcus pneumoniae Pneumococcal arthritis, right hip + Streptococcus pneumoniae Pneumococcal arthritis, left hip + Streptococcus pneumoniae
711.06 + 041.2	Pyogenic arthritis, lower leg + pneumococcus		M00.061 + B95.3 M00.062 + B95.3 M00.069 + B95.3 M00.261 + B95.3 M00.262 + B95.3 M00.269 + B95.3 M00.861 + B95.3 M00.862 + B95.3 M00.869 + B95.3 M00.169 + B95.3 M00.161 + B95.3 M00.162 + B95.3	Staphylococcal arthritis, right knee + Streptococcus pneumoniae Staphylococcal arthritis, left knee + Streptococcus pneumoniae Staphylococcal arthritis, unspecified knee + Streptococcus pneumoniae Other streptococcal arthritis, right knee + Streptococcus pneumoniae Other streptococcal arthritis, left knee + Streptococcus pneumoniae Other streptococcal arthritis, unspecified knee + Streptococcus pneumoniae Arthritis due to other bacteria, right knee + Streptococcus pneumoniae Arthritis due to other bacteria, left knee + Streptococcus pneumoniae Arthritis due to other bacteria, unspecified knee + Streptococcus pneumoniae Pneumococcal arthritis, unspecified knee + Streptococcus pneumoniae Pneumococcal arthritis, right knee + Streptococcus pneumoniae Pneumococcal arthritis, left knee + Streptococcus pneumoniae
711.07 + 041.2	Pyogenic arthritis, ankle and foot + pneumococcus		M00.071 + B95.3 M00.072 + B95.3 M00.079 + B95.3 M00.271 + B95.3 M00.272 + B95.3 M00.279 + B95.3 M00.871 + B95.3 M00.872 + B95.3 M00.879 + B95.3 M00.179 + B95.3 M00.171 + B95.3 M00.172 + B95.3	Staphylococcal arthritis, right ankle and foot + Streptococcus pneumoniae Staphylococcal arthritis, left ankle and foot + Streptococcus pneumoniae Staphylococcal arthritis, unspecified ankle and foot + Streptococcus pneumoniae Other streptococcal arthritis, right ankle and foot + Streptococcus pneumoniae Other streptococcal arthritis, left ankle and foot + Streptococcus pneumoniae Other streptococcal arthritis, unspecified ankle and foot + Streptococcus pneumoniae Arthritis due to other bacteria, right ankle and foot + Streptococcus pneumoniae Arthritis due to other bacteria, left ankle and foot + Streptococcus pneumoniae Arthritis due to other bacteria, unspecified ankle and foot + Streptococcus pneumoniae Pneumococcal arthritis, unspecified ankle and foot + Streptococcus pneumoniae

PFIZER CONFIDENTIAL

CT24-WI-GL02-RF02 5.0 Non-Interventional Study Protocol Template For Secondary Data Collection Study 01-Aug-2023

Page 34 of 46

				Pneumococcal arthritis, right ankle and foot + Streptococcus pneumoniae Pneumococcal arthritis, left ankle and foot + Streptococcus pneumoniae
711.08 + 041.2	Pyogenic arthritis, other specified sites + pneumococcus	M00.08 + B95.3 M00.28 + B95.3 M00.88 + B95.3 M00.9+ B95.3 M00.18 + B95.3	.Staphylococcal arthritis, vertebrae + Streptococcus pneumoniae Other streptococcal arthritis, vertebrae + Streptococcus pneumoniae Arthritis due to other bacteria, vertebrae + Streptococcus pneumoniae Pyogenic arthritis, unspecified + Streptococcus pneumoniae Pneumococcal arthritis, vertebrae + Streptococcus pneumoniae	
711.09 + 041.2	Pyogenic arthritis, multiple sites + pneumococcus	M00.09 + B95.3 M00.29 + B95.3 M00.89 + B95.3 M00.19 + B95.3	Staphylococcal polyarthritis + Streptococcus pneumoniae Other streptococcal polyarthritis + Streptococcus pneumoniae Polyarthritis due to other bacteria + Streptococcus pneumoniae Pneumococcal polyarthritis + Streptococcus pneumoniae	
730.0x + 041.2 730.2x + 041.2			Osteomyelitis + pneumococcus	
730.00 + 041.2	Acute osteomyelitis, site unspecified + pneumococcus	M86.00 + B95.3 M86.10 + B95.3 M86.20 + B95.3	Acute hematogenous osteomyelitis, unspecified site + Streptococcus pneumoniae Other acute osteomyelitis, unspecified site + Streptococcus pneumoniae Subacute osteomyelitis, unspecified site + Streptococcus pneumoniae	
730.01 + 041.2	Acute osteomyelitis, shoulder region + pneumococcus	M86.011 + B95.3 M86.012 + B95.3 M86.019 + B95.3 M86.111 + B95.3 M86.112 + B95.3 M86.119 + B95.3 M86.211 + B95.3 M86.212 + B95.3 M86.219 + B95.3	Acute hematogenous osteomyelitis, right shoulder + Streptococcus pneumoniae Acute hematogenous osteomyelitis, left shoulder + Streptococcus pneumoniae Acute hematogenous osteomyelitis, unspecified shoulder + Streptococcus pneumoniae Other acute osteomyelitis, right shoulder + Streptococcus pneumoniae Other acute osteomyelitis, left shoulder + Streptococcus pneumoniae Other acute osteomyelitis, unspecified shoulder + Streptococcus pneumoniae Subacute osteomyelitis, right shoulder + Streptococcus pneumoniae Subacute osteomyelitis, left shoulder + Streptococcus pneumoniae Subacute osteomyelitis, unspecified shoulder + Streptococcus pneumoniae	
730.02 + 041.2	Acute osteomyelitis, upper arm + pneumococcus	M86.021 + B95.3 M86.022 + B95.3 M86.029 + B95.3 M86.121 + B95.3	Acute hematogenous osteomyelitis, right humerus + Streptococcus pneumoniae Acute hematogenous osteomyelitis, left humerus + Streptococcus pneumoniae Acute hematogenous osteomyelitis, unspecified humerus + Streptococcus pneumoniae	

PFIZER CONFIDENTIAL

CT24-WI-GL02-RF02 5.0 Non-Interventional Study Protocol Template For Secondary Data Collection Study 01-Aug-2023

			M86.122 + B95.3 M86.129 + B95.3 M86.221 + B95.3 M86.222 + B95.3 M86.229 + B95.3	Other acute osteomyelitis, right humerus + Streptococcus pneumoniae Other acute osteomyelitis, left humerus + Streptococcus pneumoniae Other acute osteomyelitis, unspecified humerus + Streptococcus pneumoniae Subacute osteomyelitis, right humerus + Streptococcus pneumoniae Subacute osteomyelitis, left humerus + Streptococcus pneumoniae Subacute osteomyelitis, unspecified humerus + Streptococcus pneumoniae
	730.03 + 041.2	Acute osteomyelitis, forearm	M86.031 + B95.3 M86.032 + B95.3 M86.039 + B95.3 M86.131 + B95.3 M86.132 + B95.3 M86.139 + B95.3 M86.231 + B95.3 M86.232 + B95.3 M86.239 + B95.3	Acute hematogenous osteomyelitis, right radius and ulna + Streptococcus pneumoniae Acute hematogenous osteomyelitis, left radius and ulna + Streptococcus pneumoniae Acute hematogenous osteomyelitis, unspecified radius and ulna + Streptococcus pneumoniae Other acute osteomyelitis, right radius and ulna + Streptococcus pneumoniae Other acute osteomyelitis, left radius and ulna + Streptococcus pneumoniae Other acute osteomyelitis, unspecified radius and ulna + Streptococcus pneumoniae Subacute osteomyelitis, right radius and ulna + Streptococcus pneumoniae Subacute osteomyelitis, left radius and ulna + Streptococcus pneumoniae Subacute osteomyelitis, unspecified radius and ulna + Streptococcus pneumoniae
